Interested participants (caregivers) can contact us via telephone or email. One of our research associates (RA) will provide more information about the study to potential participants. An approved script including verbal consent obtained from the potential participant in order to ask them questions to determine their eligibility criteria. If the participant is eligible for the study, an appointment will be provided, and one of our interventionists will visit the participant and conduct the baseline assessment at the participants' homes in their preferred language (Spanish or English). This assessment with the caregiver will last between 2 and 3 hours. And

the assessment with the care recipient will be about 1.5 hour. In instances where assessments cannot occur in-person we will use a modified battery to conduct the assessment using a telehealth platform. These virtual visits can be broken up into two or more visits if requested by the participants. We will use paper-based forms and/or REDCap to administer the assessments.

The baseline assessment with the caregiver consists of a series of questionnaires assessing the help provided by the CG to the care recipient (e.g., ADLs/AIDLs), the level of burden, stress, and depression perceived by the CG while providing the care, the amount of social support available to the CG, and the preparedness of the CG to provide continuing care to their loved ones. The assessment with the care recipient consists of measures of depression, executive functioning (Trails A & B), working memory (Letters and Number set, digit span), processing speed (digit symbol), and verbal fluency (category fluency). In instances where the assessment is conducted virtually, certain measures may be excluded (e.g., Trails A & B, Digit Symbol). The assessment with the caregiver and care recipient might not be completed in the same visit. The study protocol allows multiple visits to complete the assessments.

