During the baseline home visit, the interventionist will go over the written informed consent with the participants (caregiver and care recipient). For virtual visits, participants will review an electronic consent form; if participants do not have a device to provide e-consent, a copy of the consent form will be mailed to the participant for signature. The assessment will not begin unless the participant has a full understanding of the informed consent form and has signed the form. In the event the care recipient can't comprehend or give consent to the assessment, the interventionist will get the assent from the caregiver. Some assessments (randomly) will be recorded for quality assurance purposes.

Upon the completion of the baseline, participants will be notified by the Project Coordinator or designee about their randomization condition: Caregiving or Health Promotion condition. During first intervention session, all participants will receive a computer tablet equipped with WiFi access. The interventionist will provide a brief tutorial on the usage of the computer tablet before starting the activities of the intervention. It is one computer tablet per dyad.

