The **Caregiving condition** will have a component for the caregiver and a component for their loved ones (the care recipient). The care recipient component will have a series of cognitive training tasks. The care recipient will meet with the interventionist on a weekly basis. The interventionist will train the care recipients on how to access these training tasks and complete homework/practice sessions. The caregiver has a total of 12 one-on-one sessions throughout the 6 months of the intervention period. Some of these sessions will be joint sessions with the care recipient. The 12 sessions will cover topics such as depression and emotional well-being; self-care and healthy behaviors; strategies for communication; strategies for mood and stress management; and strategies for management of behavioral /cognitive problems. The first, the third, and the last sessions will be at the participant's home when possible. The other sessions will be conducted via the computer tablet using videoconference program. The caregivers will also be part of 5 support group sessions where the facilitator will review the material covered in the individual sessions. For most of the part, the caregivers don't have sessions with the interventionist while the care recipients are present. Although, there will be sessions that will be conducted with both of them together because of the nature of the topic/conversation.

The **Health Promotion condition** will also have a component for the caregiver and one for the care recipient. The care recipient component will consist of mental stimulation exercises such as computer games. And the caregiver component will consist of nutrition and health promotion topics. They will have access to basic educational information from Alzheimer's Association on tips for dealing with the cognitive loss and available community resources.

Similar to participants of the caregiving condition, the caregivers of the Health Promotion condition will also have 12 one-on-one sessions with the interventionist. The first, the third, and the last sessions will be in-person when possible and the others will be via the computer-tablet using video conference program. The care recipient will have weekly sessions with the interventionist and weekly assignments as well. Caregivers and care recipients of this condition will also have some joint sessions throughout the intervention period of 6 months.

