The research team will not use undue influence or manipulation in order to recruit study participants. Our team has extensive experience in recruiting this population and is aware of the ethical conduct necessary to protect human subjects in research. There are regular meeting to monitor recruitment activities to discuss and review our recruitment practices and efforts. During recruitment activities and presentations in community events, the research team provides and explains the content of the flyer to potential participants, and answers and clarifies any questions/ concerns that potential participant may have. Interested participants are instructed and directed to call the phone number or send an email to the address display in the flyer.

11) **Setting**

The study takes place at the University of Miami Miller School of Medicine Center on Aging and the Weill Cornell Medicine Center on Aging and Behavioral Research and in the participants' homes. The intervention is technology-based, thus facilitating the communication and interaction between RAs and participants. Only study assessments (baseline, 6th month, and 12th month) and select sessions may take place at the participant's home.

In cases where a participant is unable to complete a follow-up assessment in-person, a subset of the assessments will be done by phone in order to obtain outcome measures at the proper timepoint.

12) Resources Available

All the study personnel have their CITI certificate. The PI holds regular meetings with the study coordinator and data manager to review the progress of the study. At the same time, there are weekly meetings on data management and recruitment of participants. There is also a weekly clinical team meeting of assessors who are working one-on-one with the participants to monitor and review the progress of the participants.

The Center on Aging and the Weill Cornell Medicine Center on Aging and Behavioral Research lead by [name] has extensive experience conducting research studies. Most of the members of this study are involved in other on-going studies at the Center. The Center has a computer dedicated to store and process the data. It also has secure room and cabinets to store study-related documentation. In addition, the study team contains assessors who are fully bilingual. They are fluent in both English and Spanish, thus capable of implementing the study in either language.

13) Prior Approvals

NA

14) Recruitment Methods

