The research team will not use undue influence or manipulation in order to recruit study participants. Our team has extensive experience in recruiting this population and is aware of the ethical conduct necessary to protect human subjects in research. They are all CITI certified. There are regular meetings to monitor recruitment activities to discuss and review our recruitment practices and efforts. Most of the members of the research team who have an active role in the conduct of the study (screening, assessment, and conducting the study) will also be involved in the recruitment and consent process.

During recruitment activities and presentations in community events, the research team provides and explains the content of the flyer to potential participants, and answers and clarifies any questions/ concerns that potential participant may have. Interested participants are instructed and directed to call the phone number or send an email to the address displayed in the flyer.

The study involves adults who have the capacity to consent. These potential participants are able to read and comprehend the information written in the Informed Consent Form and HIPAA authorization. Questions will be answered and addressed accordingly. Therefore no additional process will be used to obtain consent from them. Care Recipients are required to successfully respond to the Informed Consent Feedback Tool in order to be eligible for participation in the research study.

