Appendix A:

CP Program Telephone Follow-Up Assessment

Measure	# of Items
Caregiver	
ADL/IADL Modified	11
Caregiving Medical Nursing Tasks	15
*Burden Interview	12
Positive Aspects of Caregiving	11
*CESD	11
Social Support	12
Use of Formal Care and Services	Only items: 1,2, 5-8
Quality of Life	1
Caregiver Preparedness	6
Caregiving Self-efficacy	9
Caregiver Self Health Rating	Only items: 1,2
Loneliness	20
CP/Nutrition Evaluation	21
*Cognitive Decline of CR Scale	Change stem as compared to the last six months and ask items: 1 -6
Care Recipient	
Quality of Life AD	
CESD	

Before asking the scale items on the Cognitive Decline of CR Scale (items 1 – 6) Please ask the CG the following question:

•
“Compared to six months ago has your partner’s (Care recipient) cognition:

Gotten Much Worse, (2) Gotten Slightly Worse, (3) Stayed the Same, (4) Gotten Slightly Better (5)
Gotten Much Better?

At the end of the Evaluation for CP ask the CG in the CP condition the following questions:

To what extent did your partner use the organizational tool?

(1) Very frequently (2) Frequently (3) Occasionally (4) Rarely (5) Never

How often did your partner do the computer exercises?

(1) Very frequently (2) Frequently (3) Occasionally (4) Rarely (5) Never

I found the organizational tool valuable?

(1) Strongly agree (2) Agree (3) Neither agree or disagree (4) Disagree (5) Strongly Disagree

The computer exercises were beneficial for my partner

(1) Strongly agree (2) Agree (3) Neither agree or disagree (4) Disagree (5) Strongly (2) Disagree

At the end of the Evaluation for CP ask the CG in the Nutrition condition the following questions:

How often did your partner do the computer exercises?

(2) Very frequently (2) Frequently (3) Occasionally (4) Rarely (5) Never

The computer exercises were beneficial for my partner

(3) Strongly agree (2) Agree (3) Neither agree or disagree (4) Disagree (5) Strongly Disagree

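### The plan shares assessing and treating roles without saying who collects the 6- and 12-month outcomes or whether they are masked, and the telephone form lists an arm-specific evaluation ahead of three outcomes

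*Combined protocol and SAP*

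**What the plan says.** **Baseline.** Section 5 (Procedures Involved) states that "one of our interventionists will visit the participant and conduct the baseline assessment". Allocation is disclosed afterwards: "Upon the completion of the baseline, participants will be notified by the Project Coordinator or designee about their randomization condition".

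**Delivery.** Section 5 gives the interventionist the treatment contact in both arms. In the Caregiving condition, "The care recipient will meet with the interventionist on a weekly basis", and the caregiver has 12 individual sessions. In the control arm, "the caregivers of the Health Promotion condition will also have 12 one-on-one sessions with the interventionist", and care recipients again have weekly sessions.

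**Assessors.** Section 12 (Resources Available) refers to a "weekly clinical team meeting of assessors who are working one-on-one with the participants to monitor and review the progress of the participants". Section 18 (Consent Process) treats assessment and study conduct as activities of one team: "Most of the members of the research team who have an active role in the conduct of the study (screening, assessment, and conducting the study".

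**Follow-up.** Section 5 times the two follow-up assessments at 6 and 12 months from session 1 and names no one to do them. Section 11 allows a reduced set by telephone when an in-person follow-up is not possible.

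**Telephone form.** Appendix A lists a 21-item "CP/Nutrition Evaluation". It comes directly before the Cognitive Decline of CR Scale and before the two care-recipient measures, Quality of Life AD and CESD. Its closing questions depend on condition: four for the Caregiving arm and two for the Nutrition arm.

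**The concern.** The hypotheses in Section 2 rest largely on reported distress, burden and quality of life, and on tests given to the care recipient by an examiner. Such outcomes can move with the expectations of the person collecting them and with the respondent's wish to please that person. If the follow-up assessor delivered the dyad's sessions, staff allegiance to the experimental programme, or a participant's courtesy towards the person who delivered it, could shift scores towards DT. The 6-month visit falls just as the 6-month delivery period ends, when that relationship is freshest.

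Appendix A adds a second route. The interviewer cannot choose the right closing questions without knowing the arm. Taken in list order, the form therefore reveals the arm before three outcomes. It also asks the caregiver whether the computer exercises helped her partner just before she rates how her partner's cognition has changed. That rating is the only measure of care-recipient cognition on the telephone form.

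**Working it through.** The plan gives no figure on this point to reproduce. The check sets the provisions side by side and then shows what an assumed bias would do.

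**Roles**

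| Step | Who does it | Arm known? |
|---|---|---|
| Baseline | An interventionist (Section 5) | No; disclosed after baseline |
| Sessions over 6 months | Interventionist, both arms (Section 5) | Yes |
| Weekly progress review | Assessors (Section 12) | Not stated |
| 6 and 12 months | Not stated | Not stated |

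Baseline shows that assessing is part of the interventionist's job. Section 12 shows that assessors follow participants' progress during treatment. No available provision separates the last row from the second.

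**Order of Appendix A**

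- Before the evaluation: caregiver burden, caregiver CESD, quality of life, preparedness, self-efficacy and others. List order cannot affect these.
- After the evaluation: the Cognitive Decline scale, then the care recipient's Quality of Life AD and CESD. On all three the interviewer would know the arm.
- The added questions go to the caregiver, so only the caregiver-rated Cognitive Decline scale can be primed by them.
- Both arms are asked how often the exercises were done and whether they helped. Only the Caregiving arm is also asked about use and value of the organizational tool (4 − 2 = 2 extra questions). Priming is therefore partly common to both arms and partly not.

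**Illustration of size**

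Assumptions: no true effect; a shift of b SD favouring DT; 1:1 allocation (ratio not stated); a two-sided 5% test of two means (no level is given for the main test). Section 2 randomises 240 dyads, or 240/2 = 120 per arm. Section 15 counts 120 dyads, or 120/2 = 60 per arm. Both are shown.

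SE = √(2/n) in SD units. Rejection rate = P(Z > 1.96 − b/SE) + P(Z < −1.96 − b/SE).

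Example, n = 120 and b = 0.2: SE = √(2/120) = 0.129; b/SE = 1.549; P(Z > 0.411) = 0.341; the other tail is negligible.

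| n per arm | SE | b = 0.1 | b = 0.2 | b = 0.3 |
|---|---|---|---|---|
| 60 | 0.183 | 8.5% | 19.5% | 37.6% |
| 120 | 0.129 | 12.1% | 34.1% | 64.2% |

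The nominal rate is 5%. In the DT direction alone the rates are 7.9%, 19.4% and 37.6% with 60 per arm, and 11.8%, 34.1% and 64.2% with 120, against 2.5%. The documents give no basis for any particular b. A larger trial does not help: a fixed bias is more likely to reach significance as n grows.

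**The case against.** The strongest reply is that the documents never say the treating interventionist performs follow-up. A reader might infer it from the baseline sentence, but baseline precedes disclosure of the arm and so cannot itself carry bias from knowing it. A reader might also infer it from Section 12, but individual contact could mean assessment contact only. Both points stand. What is left is that the role is unassigned and unmasked in a team where the roles overlap.

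Second, the control was chosen to match contact time, and its dyads also see an interventionist throughout. It is tempting to say that rating one's distress to a familiar coach favours DT. The design does not support that, because familiarity exists in both arms. A differential shift needs staff expectation or allegiance, or participants wanting to please the person who delivered the programme. The first two are plausible because only one programme is under test, but the documents do not quantify any of them.

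Third, Appendix A is a list of measures and does not expressly fix an order. It applies only to telephone follow-up. It contains neither HVLT-R, the patient primary outcome named in Section 7, nor any examiner-scored test. Caregiver CESD, the caregiver primary outcome named there, is listed before the evaluation. It would be wrong to conclude that list order compromises either named primary outcome. The ordering point is confined to the three measures listed after the evaluation.

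Fourth, participants know their programme, so a masked assessor protects self-report only in part. That limits the benefit but does not remove it.

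**Conclusion.** The concern holds as a gap in the plan and as a fault in the order of one form. The available text neither names nor masks the follow-up assessor, and it permits the person who treated a dyad to collect that dyad's outcomes. If the telephone form is followed as listed, the interviewer learns the arm before three outcomes, and the caregiver's cognitive-decline rating can be primed.

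The documents do not show that treating staff actually collect follow-up outcomes, or that results are biased towards DT. The error rates above are conditional on assumed shifts and are not estimates for this trial. Three limits apply: part of the document between Section 19 and Appendix A was not available, the in-person form is not included, and the proportion of telephone follow-ups is unknown. Confidence is moderate. The change is worth making because it is specific and its cost is small.

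**What to change.** 1. **Order and ownership of the evaluation.** In Appendix A, and in any in-person form with the same order, place the programme evaluation and its arm-specific questions after every caregiver and care-recipient outcome. Have someone other than the outcome assessor give them. Failing that, use a different assessor at 12 months; otherwise the person unmasked at 6 months goes on to assess the same dyad.

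2. **Follow-up assessor.** State in Section 5 that the 6- and 12-month outcomes are collected by an existing team member who did not deliver that dyad's sessions, is not told its arm, and does not attend the weekly progress review of that dyad. If this is already the practice, a short statement will document it.

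3. **Keep the mode of assessment.** Retain in-person assessment where it is planned, and use staff from the other site only for visits that would be remote anyway. Section 5 allows Trails A & B and Digit Symbol to be dropped from virtual assessments, and the telephone form has no cognitive testing, so moving visits to remote assessment for the sake of masking could lose Aim 2 data.

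The cost is a re-ordered form, scheduling effort, and a second person to give the evaluation. Team size is not stated, so it is an assumption that existing staff at the two sites can cover this. Self-reported outcomes would still be only partly protected.

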After IRB approval the research team will contact potential recruitment sites and inform them about the study. These sites will be provided with IRB approved promotional materials (flyer) for recruitment. At the same time, the WCM PR department will be informed and notified of the ongoing research. The PR department will be provided with the promotional materials for the study. WCM sites such as those that make regular postings and newsletters will also be contacted and provided with an approved ad or communication regarding the project. The CITI certified staff members within the project plan to also attend health fairs and /or senior centers and events and have flyers available at various community centers so that potential participants can learn of the study. The WCM approved ad will also be posted in non-WCM newsletters and advertisement sections. Promotional material used in this study are: flyer, radio ad and advertisement blurb.

IRB-approved letters may be sent to designated patients from WCM/NYPH clinics with IRB approval.

Once potential participants learn of the study, they will phone the recruitment phone line. A brief telephone interview will be conducted. If these participants are eligible for the study, they will then be scheduled for the baseline assessment.

Participants will not have any financial liabilities for participating in the study. The study provides financial compensation for their time/effort in completing the assessment. Eligible caregiver participants will receive \$30 for each completed assessment, for a total of \$90 (\$30 at baseline, 6-month, 12-month visits). Eligible care recipient participants will receive \$20 for each completed assessment, for a total of \$60 (\$20 at baseline, 6-month and 12-month visits). \$10 will be provided to those that do not meet eligibility.

15) Local Number of Subjects

We anticipate to screen a maximum of 350 participants. We expect 240 participants (120 dyads) to complete the study. 80 participants will be from University of Miami and 160 will be from the Weill Cornell Medicine Center on Aging and Behavioral Research.

16) Confidentiality

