When a person (caregiver), who is interested in the study contacts us via telephone or email to request information, a trained and certified screener/assessor will call the participant back and explain the basics of the study. Then they will ask the participant's permission to proceed with the telephone screening questionnaire that would lead us to make a decision as to whether or not he or she might be an appropriate candidate for the study or basically would qualify for the study. This process is a preliminary screening done over the telephone, which is not feasible to do by having a written consent. If and only when a person 1) has agreed to be screened over the phone; 2) understands that this study represents research; and 3) understands their participation is voluntary and that they can withdraw their consent at any time, will the screening process proceed. We will not obtain a written consent form for the phone screening process as this research presents no more than minimal risk of harm to subjects and involves no procedures for which written consent is normally required outside of the research context (45 CFR 46.117 (c) (2). It is not possible to have written consent from each potential participant for practical as well as cost reasons.

Upon the completion of the telephone screening and if the participant appears eligible for the study, a home or virtual visit by one of the research team members (CITI certified) will be scheduled. A written informed consent form will be obtained by the CITI-certified and protocol trained RA during the first visit. Before any additional study-specific information is obtained, participants will be asked to read the IRB-approved consent form. The potential participant is asked to read the consent form and, if agreeable to participate, sign it in the presence of an assessor. If consenting virtually, the participant will follow the IRB-approved method.

During the phone screening process and other screening steps and after the potential participant verbally consents to participating in the study, they will be scheduled for an appointment for a baseline assessment.

19) Process to Document Consent in Writing

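### Section 5 lets a caregiver's assent stand in for a care recipient who cannot consent to baseline testing, while section 18 makes that care recipient ineligible

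*Combined protocol and SAP*

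**What the plan says.** Section 5 (Procedures Involved) describes the baseline home visit. The interventionist reviews the consent form with both members of the dyad, and testing is not to start until the participant understands the form and has signed it. The next sentence deals with a care recipient who cannot meet that standard. If the care recipient cannot "comprehend or give consent to the assessment, the interventionist will get the assent from the caregiver".

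Section 18 (Consent Process) takes a different position. It says: "The study involves adults who have the capacity to consent". It concludes that nothing further is needed to obtain their consent. It then adds a condition specific to care recipients: "Care Recipients are required to successfully respond to the Informed Consent Feedback Tool in order to be eligible for participation in the research study". It states no exception.

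On timing, section 18 also says: "Before any additional study-specific information is obtained, participants will be asked to read the IRB-approved consent form". On burden, section 5 says that "the assessment with the care recipient will be about 1.5 hour". Where testing is virtual the battery is modified, and its length is not given.

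**The concern.** The two sections treat the same person differently. Under section 18, a care recipient who cannot show understanding of the consent form is not eligible. Under section 5, the caregiver's agreement is sought in that person's place, and the only evident purpose is to let the assessment go ahead.

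The situation is foreseeable. Section 4 admits care recipients partly because they show memory problems, and section 5 itself anticipates that some will not comprehend the form. Section 14 calls for recruitment by more than one route and section 15 names two centres, so assessors could in good faith follow different sections. One would test a person whom another would turn away. At stake are the protection of a person with impaired memory and having one clear rule on who undergoes research testing.

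**Working it through.** No arithmetic applies. The check sets the provisions side by side for one person: a care recipient who, at the baseline visit, cannot comprehend the consent form.

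1. **Section 5.** The sentence requiring understanding and a signature would stop the assessment. The assent sentence that follows can be read as an exception to it, so section 5 can be consistent within itself and no separate conflict is counted there. The assent sentence does not say outright that testing then proceeds, but it gives the assent no other function.

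2. **Section 18.** This person falls outside the stated population of adults with capacity. The caregiver's assent would also be an added consent process, which section 18 says is not used. Finally, the person would have to pass the Feedback Tool. The documents do not describe the Tool's content. The assumption here is that someone who cannot comprehend the form would not respond to it successfully.

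3. **Sequence.** The documents give this order: a telephone screen with the caregiver, which section 18 calls preliminary; a home or virtual visit, with the consent form read before more study information is collected; the baseline assessment; and enrolment and random assignment following baseline (section 5). The Feedback Tool is not placed anywhere in this sequence in the available text.

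4. **Two possible placements of the Tool.**
   - If it comes before the battery, a care recipient who cannot comprehend the form has already been found ineligible. The assent sentence then has nobody to apply to at baseline, yet it still tells staff to seek assent.
   - If it comes after the battery, the person undergoes about 1.5 hours of in-person research testing on the caregiver's assent and is then found ineligible.

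   Under either placement, sections 5 and 18 need to be reconciled.

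5. **Section 4.** The care-recipient criteria cover the MMSE range, need for help with higher-level daily activities, memory problems and, for those scoring high on the MMSE, the CDR. They mention neither the Tool nor capacity, so they do not decide which section governs.

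**The case against.** The strongest reply is that section 5 is limited to the assessment and section 18 to participation in the study. On this view assent permits testing, ineligibility is found at or after the visit, and nobody without capacity is enrolled. Two provisions support it: section 5 puts enrolment after baseline, and section 14 says that $10 "will be provided to those that do not meet eligibility". Much of this stands. A reader might infer that staff would go on to randomize such a person, but the documents do not support that. The assent sentence does not waive the eligibility condition in section 18, and staff applying both sections would not randomize the person. What the reply does not remove is the testing itself. The baseline battery is research testing, and section 18 foresees no substitute consent for it.

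A reader might also infer that care-recipient eligibility is already settled by telephone, because section 5 says "If the participant is eligible for the study, an appointment will be provided" and section 14 says "If these participants are eligible for the study, they will then be scheduled for the baseline assessment". That inference fails too. The telephone screen is a preliminary one held with the caregiver, and the care recipient still has to meet an MMSE criterion.

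The assent sentence might instead be meant for the 6- and 12-month visits, when a care recipient who was eligible at entry may have declined. The paragraph opens with the baseline home visit, so this is not the natural reading.

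Lastly, section 19, on documenting consent in writing, was not available to this review. It may say when the Tool is given or how assent is recorded. That lowers confidence but does not undo a conflict between two sections that are present.

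**Conclusion.** The conflict holds and should be fixed. A care recipient who is ineligible under section 18 has, under section 5, a route into the baseline battery on the caregiver's assent, and the available text does not say whether the Feedback Tool would come first.

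Per affected person, the size is about 1.5 hours of research testing in person, and an unstated length if virtual. The number of people cannot be estimated from the documents. The conclusion rests on reading the assent as permission to proceed, and on the assumption that failure to comprehend the form means failure on the Tool. Confidence is moderate, chiefly because section 19 could not be read.

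A reader might take this as a threat to the trial's results. Nothing in the documents supports a claim of bias, and the analysis is unaffected.

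**What to change.** Reconcile sections 5 and 18 to one rule, chosen by the sponsor and the IRB. There are two ways to do it:

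- Remove the caregiver-assent sentence from section 5, so that the Feedback Tool condition in section 18 stands alone.
- If a surrogate route is intended, define it in section 5 (who may act, and how the care recipient's own agreement is recorded), and amend the capacity, consent-process and Feedback Tool sentences in section 18 to match.

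Under either choice, state that the Tool result is obtained before the care-recipient battery or, if it is not, when it is obtained. Add the rule to the care-recipient criteria in section 4 and check it against section 19.

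The cost is a few sentences, mainly in sections 5 and 18 with a line in section 4, and an IRB amendment. Removing the assent sentence may produce a few more screen failures, in a number the documents do not allow to be estimated. The analysis plan does not change.
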